7.1. Overall Statistical Consideration

In the statistical tabulations, screening number of subjects is the universal unique identifier of subjects in the study.

General rules of descriptive statistics: Quantitative variables are described by mean, standard deviation, median, minimum, maximum, Q1 and Q3. In terms of rounding, the numbers of decimal places of the minimum and maximum are consistent with that of original value, while those of mean, medium, Q1, and Q3 are 1 more than that of the original value, and that of standard deviation is 2 more than that of the original value. Categorical variables are described by number and percentage of each category. The number of subjects is rounded to integer and percentage is rounded to one decimal place. It is unnecessary to present a percentage when the count is 0.

General rules of inferential statistics: Two-sided test is adopted for all statistical tests (unless otherwise specified). $P < 0.05$ will be considered statistically significant (unless otherwise specified). P value is rounded to 4 decimal places. If $P < 0.0001$, it is presented as ' $< .0001$ '; if $P > 0.9999$, it is presented as ' $> .9999$ '.

For primary analysis, the baseline of efficacy analysis is defined as the last available value before randomization in Stage 1, and the baseline of safety analysis is defined as the last available value before the first dose in Stage 1.

For the analysis in Stage 2, one group of baselines is defined for efficacy analysis and two groups of baselines are defined for safety analysis. The baseline of efficacy analysis is defined as the last available value before randomization in Stage 1. The baseline of safety analysis in Group 1 is defined as the last available value before the first dose. The baseline of safety analysis in Group 2 is defined as the last available value before the first dose in Stage 2. Efficacy analysis will be performed using the baseline of Group 1. Safety analysis will be performed to analyze the changes from baseline in laboratory test, ECG and vital signs at each visit using the baseline of Group 1 and the baseline of Group 2, respectively.

Statistical analyses will be performed using SAS 9.4.

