12.5. Analysis Plan

Statistical analyses will be performed using SAS 9.4 or higher version.

Descriptive statistics will be used to summarize demographics, baseline characteristics, exposure, safety data, PK and PD data. For continuous variables, descriptive statistics will include the number of observed subjects, the number of subjects with missing observations, mean, SD, standard error, minimum, median, maximum, frequency, and percentage. For lognormally distributed data, the geometric mean, geometric standard deviation and geometric coefficient of variation will be calculated. For categorical variables or ordinal data, the frequency and percentage of each category will be listed.

For changes in continuous variables from baseline, the results will be presented according to their corresponding post-baseline visits. All research data and other clinically significant data used to generate tables and figures will be listed by treatment group, subject, and time point.

Definition of baseline:

Primary analysis: The baseline of efficacy analysis is defined as the last available value before randomization in Stage 1, and the baseline of safety analysis is defined as the last available value before the first dose in Stage 1.

Stage 2 analysis: Two sets of baselines are defined.

- The first set of baselines: the baseline of efficacy analysis is defined as the last available value before randomization in Stage 1, and the baseline of safety analysis is defined as the last available value before the first dose.
- The second set of baselines: The baseline of efficacy analysis is defined as the last available value before randomization in Stage 2 or before entering Group E, and the baseline for safety analysis is defined as the last available value before the first dose in Stage 2.

After the 255 subjects enrolled based on the V2.1 and prior versions of the protocol complete the administration and treatment, related evaluations and follow-up of Stage 1 (W16 pre-dose visit), the primary analysis will be performed.

For subjects entering stage 2 study, analyses will be performed based on the baseline of the two groups.

During the primary analysis, the W16 data will be unblinded and statistically analyzed. The statistically significant type I error level of the primary efficacy endpoint analysis is set at 0.05 (two-sided test).

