4.1.2. Secondary endpoints

Key secondary endpoints

- The proportion of subjects achieving EASI-75 at W16;
- The proportion of subjects whose weekly average PP-NRS is decreased by ≥ 4 points from baseline at W16;
- The proportion of subjects whose weekly average PP-NRS is decreased by ≥ 3 points from baseline at W16;
- Change and percentage change in the weekly average PP-NRS from baseline at W16;
- The proportion of subjects achieving EASI-90 at W16.

Other secondary endpoints

- Change and percentage change in the EASI score from baseline at W16;
- The proportion of subjects achieving EASI-50 at W16;
- Percentage change in the BSA of AD involvement from baseline at W16;
- Percentage change in the SCORAD score from baseline at W16;
- Change in DLQI from baseline at W16;
- Change in POEM from baseline at W16;
- Percentage change in the weekly average PP-NRS from baseline at W2;

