7.4. Efficacy Analysis

Efficacy analysis in Stage 1 will be performed based on FAS1 and PPS1, mainly the FAS1.

In order to control the type I error rate for multiplicity, a fixed-sequence method will be used. First of all, the active treatment group and the placebo group will be compared for the primary efficacy endpoint; when the primary efficacy endpoint reaches statistical significance, the active treatment group and the placebo group will be compared for the key secondary efficacy endpoints according to the sequence specified in the protocol.

Efficacy analysis in Stage 2 will be performed based on FAS2.

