7.4.4. Other efficacy endpoint analysis

The categorical efficacy endpoint analysis in Stage 1 will be performed using the same method as the primary efficacy endpoint analysis.

The continuous efficacy endpoint analysis in Stage 1 will be performed using the same method as the secondary efficacy endpoint analysis.

According to the investigator's judgment, AD aggravation or deterioration of symptoms which requires drugs or treatments originally prohibited by the protocol for rescue therapy will be defined as "AD recurrence" event.

The number of AD recurrence, the number of subjects with AD recurrence, and the number of days of AD recurrence in Stage 1, from baseline to W8, from W9 to W16 will be analyzed. The total number of AD recurrence in each stage will be summarized. AD recurrence will be summarized by the number of recurrences, that is, 0, 1, 2 and ≥ 3 . The number and percentage of subjects will be calculated. Chi-squared test will be adopted to compare whether the differences between the two groups are statistically significant. The total number of subjects with AD recurrence in each stage will be summarized, and the number and percentage of subjects will be calculated. Chi-squared test will be performed to compare whether the differences between the two groups are statistically significant. The number of days of AD recurrence in each stage will be summarized by descriptive statistics.

7.4.5. Efficacy analysis in stage 2

During efficacy analysis in Stage 2, the percentage of subjects achieving efficacy endpoint and its confidence interval will be calculated for categorical efficacy endpoints. For continuous efficacy endpoints, ANCOVA model will be used to calculate the mean, the Least Square Mean, 95% confidence interval and SE of the change from baseline and percentage change from baseline of each efficacy endpoint. The model will include treatment group, severity of baseline disease (IGA 3 or 4), and baseline value of corresponding endpoint. Inferential statistics will not be performed during the Stage 2 analysis. The following two analyses will be performed.

Analysis method 1: Categorical efficacy endpoints after the occurrence of events will be regarded as no response for subjects who have the following conditions; continuous efficacy endpoints after the occurrence of events will be imputed using WOCF in Stage 2; other missing data except for the conditions above will be imputed using multiple imputation (MI).

- Group adjustment

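### SAP 7.1 and 7.4.4 allow Stage 1 tests outside the fixed sequence, most clearly those on AD recurrence, to be called statistically significant with no gate and no nominal label

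*SAP*

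**What the plan says.** SAP 7.1 gives the general rules of inferential statistics. "Two-sided test is adopted for all statistical tests (unless otherwise specified"), and a P value below 0.05 "will be considered statistically significant (unless otherwise specified"). SAP version 1.0 has the same rule.

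SAP 7.4 states the multiplicity control: "In order to control the type I error rate for multiplicity, a fixed-sequence method will be used". The gate is that "when the primary efficacy endpoint reaches statistical significance, the active treatment group and the placebo group will be compared for the key secondary efficacy endpoints", in the protocol's order. Protocol 12.7.1 has the same scope. Protocol 12.5 sets the level for one endpoint: "The statistically significant type I error level of the primary efficacy endpoint analysis is set at 0.05 (two-sided test").

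SAP 4.1.2 and 4.1.3 then list other secondary and other efficacy endpoints, which are not in the sequence. SAP 7.4.4 covers their Stage 1 analysis. For categorical endpoints, "The categorical efficacy endpoint analysis in Stage 1 will be performed using the same method as the primary efficacy endpoint analysis", which is the stratified CMH test. Continuous endpoints follow the secondary-endpoint method, which is the MMRM. For AD recurrence, "Chi-squared test will be adopted to compare whether the differences between the two groups are statistically significant". That instruction is given for subjects classified by number of recurrences (0, 1, 2, ≥3), and again in almost the same words for the number of subjects with any recurrence. The windows are all of Stage 1, baseline to W8, and W9 to W16.

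Stage 2 is expressly exempt from inference (SAP 7.4.5, Protocol 12.5).

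**The concern.** The rule in 7.1 is a default that applies unless another passage displaces it. The fixed sequence displaces it for the key secondary endpoints, and the no-inference statement displaces it for Stage 2. Nothing displaces it for the remaining Stage 1 endpoints: they have no gate on the primary, no share of alpha, and no nominal or exploratory label. For AD recurrence the SAP goes further and makes a significance judgement the purpose of the test.

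At stake is what the report may say. If the primary or an early key secondary endpoint failed, formal testing in the sequence would stop. The other secondary and recurrence analyses would still run, and under 7.1 any P below 0.05 among them would be called statistically significant. That sits badly with a section that says it controls type I error for multiplicity.

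**Working it through.** **Which rule reaches which endpoints**

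| Endpoints | Gate or exemption | Output the SAP names | 7.1 default applies? |
|---|---|---|---|
| Primary | First in the sequence, 0.05 | CMH test, difference, 95% CI | Yes, as intended |
| Key secondary | Gated (7.4) | CMH or MMRM | Only when reached |
| EASI-50 at W16 | None | CMH test, difference, 95% CI | Yes |
| Seven continuous other secondary | None | LS means, 95% CIs (7.4.3) | Only if P values are produced |
| AD recurrence, Stage 1 | None | Chi-squared, to judge significance | Yes, explicitly |
| Stage 2 endpoints | No inference | Estimates, CIs | No |

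For the seven continuous endpoints, P values are an inference. The protocol synopsis (statistical analysis methods) says between-group comparisons of continuous endpoints use MMRM, but the SAP mentions only LS means and intervals.

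**Count**

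- Other secondary (SAP 4.1.2): seven bullets, but "Change and percentage change in the EASI score from baseline at W16" holds two endpoints, so 8. The others are EASI-50, BSA, SCORAD, DLQI, POEM and PP-NRS at W2.
- AD recurrence: 2 tables × 3 windows = 6 chi-squared tests. Days of recurrence are descriptive and not counted.
- Total: 8 + 6 = 14. This omits IGA decrease of ≥2 points, EASI-100, by-visit changes, and the ANOVA tests on ECG and vital signs.

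**The plan's own figure**

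The plan gives no error rate for these tests. Its related figure is 90% power for the primary at two-sided 0.05, with 27% versus 9% in 144 and 72 completers (Protocol 12.3).

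- Pooled rate: (144 × 0.27 + 72 × 0.09)/216 = 0.21
- SE under the null: √[0.21 × 0.79 × (1/144 + 1/72)] = 0.0588
- SE under the alternative: √[0.27 × 0.73/144 + 0.09 × 0.91/72] = 0.0501
- Power: Φ[(0.18 − 1.96 × 0.0588)/0.0501] = Φ(1.29) = 0.902

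The figure reproduces. Nothing below changes it.

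**Chance of at least one P below 0.05 with no drug effect**

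For k independent tests it is 1 − 0.95^k, either direction: k = 8 gives 0.337 and k = 14 gives 0.512. For results favouring CBP-201 it is 1 − 0.975^k: 0.183 and 0.298. The documents give no correlation, so the other rows come from simulating equally correlated two-sided z-tests (200,000 draws).

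| Assumed correlation | 8 tests, either direction | 14 tests, either direction | 8 tests, favouring CBP-201 | 14 tests, favouring CBP-201 |
|---|---|---|---|---|
| 0 | 34% | 51% | 18% | 30% |
| 0.3 | 30% | 44% | 15% | 23% |
| 0.5 | 25% | 35% | 12% | 18% |
| 0.8 | 16% | 20% | 8% | 10% |
| 0.9 | 12% | 14% | 6% | 7% |

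For the six recurrence tests alone, which need no inference about whether P values exist, independence gives 1 − 0.95^6 = 26.5%. That is a high figure, because these tests overlap heavily.

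**The case against.** The best defence is that the confirmatory scope is already clear. There is one formal hypothesis (Protocol 12.2, SAP 5), the 0.05 level is set for the primary, and the tiers imply that whatever lies below key secondary is supportive. The 7.1 sentence sits beside rules on rounding and display, and calling a P value significant is not the same as claiming efficacy. This is also a Phase II trial, and the change alters no estimate.

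Part of this stands. A reader might infer that every P value in the trial is uncontrolled. The documents do not support that: the rule yields where something else is specified, key secondaries are gated, and Stage 2 has no inference. A reader might also set 25% or 35% against a promised 5%. No passage promises a 5% familywise level over these 14 tests, so no stated guarantee is broken.

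The objection to the arithmetic also stands. EASI change and percentage change use the same measurements. The whole-Stage 1 window contains both sub-windows, and any-recurrence collapses the count table. The four-category table gives a chi-squared test with up to 3 degrees of freedom and no single direction. An equicorrelated z-model only approximates this, and the figures near independence are unrealistic.

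What does not stand is that tiering alone settles the matter. Tiering leaves the label to be inferred, whereas 7.1 supplies a label and 7.4.4 asks for a significance verdict on recurrence. Where the authors wanted no inference, in Stage 2, they said so.

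**Conclusion.** The point holds for Stage 1 endpoints outside the fixed sequence. Followed as written, the plan permits uncontrolled statements of statistical significance there, whatever the primary result. AD recurrence is the clearest case because its text asks for that judgement. EASI-50 follows from the CMH method. The seven continuous other secondary endpoints are affected only if MMRM P values are reported.

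Type I error for the primary and key secondary sequence is intact, so it would be wrong to infer that the confirmatory result is compromised. The chances (12–34% for 8 tests and 14–51% for 14, either direction; for 14 tests favouring CBP-201, about 7% at correlation 0.9 and 18% at 0.5) rest on no drug effect, P values for all tests counted, and an assumed common correlation. They show scale and do not estimate this trial's error rate. The defect is one of labelling, but it governs what may be concluded and is cheap to close.

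**What to change.** In SAP 7.1, limit the term statistically significant to the primary endpoint and to key secondary endpoints reached in the fixed sequence. Add that all other Stage 1 P values (other secondary, other efficacy, AD recurrence) are nominal and support no claim of significance, whatever the primary result.

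In SAP 7.4.4, replace the stated purpose of both chi-squared comparisons with a nominal P value and a 95% CI for the difference. The four-category table has no single difference, so give percentages by category with the nominal P value.

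This costs wording only: the primary alpha (0.05), power (0.902) and planned 255 subjects do not change. The downside is that these endpoints can no longer be reported as statistically significant. Because the change only withdraws claims, it introduces no bias even if made after Stage 1 unblinding, and Protocol 12.1 already provides for discussing departures from the SAP in the study report.

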RS2 will include all subjects who have been randomized to Group C or D and all subjects assigned to Group E.

RS2_R: RS2_R will include all subjects who have been randomized to Group C or D.

RS2_NR: RS2_NR will include all subjects who have been assigned to Group E.

Full analysis set 2 (FAS2)

FAS2 will include all subjects who have been randomized to Group C or D and all subjects who have been assigned to Group E and received at least one dose of the study drug in Stage 2. Subjects are analyzed within FAS2 according to treatment assigned.

FAS2_R: FAS2_R will include all subjects who have been randomized to Group C or D and received at least one dose of the study drug for Stage 2.

FAS2_NR: FAS2_NR will include all subjects who have been assigned to Group E and received at least one dose of the study drug for Stage 2.

Safety set 2 (SS2)

SS2 will include all subjects in RS2 who have received at least one dose of the study drug for Stage 2. Subjects are analyzed within SS2 according to the treatment they actually received.

Safety set 3 (SS3)

SS3 will include all subjects in SS1 and SS2 who have received at least one dose of the study drug.

PK set 2 (PKS2)

PKS2 will include all subjects who have received at least one dose of CBP-201 active drug for Stage 2 and have at least 1 collected and analyzable PK sample for Stage 2.

For the supplementary analysis based on all subjects (including the 75 subjects newly enrolled), the definitions of analysis sets are the same as above.

Table 4: Analysis Population, Treatment Group and Analysis Stage

Analysis Populations	Treatment Groups	Analysis Stage
RS1/ FAS1/ PPS1/ SS1	1) Placebo 2) CBP-201 300 mg Q2W	Stage 1 treatment period.
RS2_R/ FAS2_R	1) Placebo/CBP-201 300 mg Q2W 2) Placebo/CBP-201 300 mg Q4W 3) CBP-201 300 mg Q2W/CBP-201 300 mg Q2W 4) CBP-201 300 mg Q2W/CBP-201 300 mg Q4W 5) Q2W Total 6) Q4W Total 7) Total	From the completion of Stage 2 randomization to the end of study for subjects who have completed Stage 1 and been randomized to Group C or D.
RS2_NR/ FAS2_NR	1) Placebo/CBP-201 300 mg Q2W 2) CBP-201 300 mg Q2W/CBP-201 300 mg Q2W 3) Open-Label Q2W Total	From the start of Stage 2 to the end of study for subjects who have completed Stage 1 and been assigned to Group E.
SS2	1) CBP-201 300 mg Q2W (Group C) 2) CBP-201 300 mg Q4W (Group D)	From the first dose for Stage 2 to the end of Stage 2.

	3) CBP-201 300 mg Q2W (Group E) 4) Total	

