SS3	1) CBP-201 300 mg Q2W 2) CBP-201 300 mg Q2W/CBP-201 300 mg Q4W 3) CBP-201 300 mg Q2W/CBP-201 300 mg Q4W/CBP-201 300 mg Q2W 4) CBP-201 300 mg Q4W 5) CBP-201 300 mg Q4W/CBP-201 300 mg Q2W 6) Total	It includes all subjects who have received at least one dose of CBP-201 from Stage 1 to Stage 2. From the first dose of CBP-201 to the end of study.

7. Statistical Methods

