7.5.3. Laboratory test results

Analysis will be performed based on SS1, SS2 and SS3. Analysis will not be performed using SS3 by visit.

The hematology, blood biochemistry and urinalysis parameters at baseline and each visit and their changes from baseline at each visit will be summarized by descriptive statistics.

The number and percentage of subjects whose hematology, blood biochemistry and urinalysis parameters at baseline and each visit are below, within and above the normal range will be summarized.

Pre-treatment and post-treatment laboratory test results are classified into abnormal with clinical significance, abnormal without clinical significance, normal, and not tested in an order of abnormal with clinical significance > abnormal without clinical significance > normal > not tested. Then shift tables are generated. The shift tables are generated based on CTCAE 5.0.

All laboratory test results and abnormal laboratory test results for hematology, blood biochemistry, urinalysis and urine pregnancy will be tabulated.

Qualitative laboratory test results will be summarized by visit. The number and percentage of subjects for each category will be calculated and tabulated.

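### SS3 starts at the first CBP-201 dose, but neither safety baseline in SAP 7.1 is the pre-CBP-201 value for everyone in it, and none is assigned to the SS3 shift tables and QTcF-increase counts

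*SAP*

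**What the plan says.** All SAP references are to the later SAP version, which covers both stages.

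**Baselines.** SAP 7.1 sets out two safety baselines for the Stage 2 analysis. Group 1 and Group 2 are names for the baselines, not for sets of subjects.
- First: "The baseline of safety analysis in Group 1 is defined as the last available value before the first dose".
- Second: "The baseline of safety analysis in Group 2 is defined as the last available value before the first dose in Stage 2".

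Their stated use is to analyse "changes from baseline in laboratory test, ECG and vital signs at each visit using the baseline of Group 1" and, separately, the second baseline. Protocol 12.5 words its first set the same way: "the baseline of safety analysis is defined as the last available value before the first dose". No baseline in either document is tied to the first dose of CBP-201.

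**SS3.** SAP section 6, Table 4, describes the population as "It includes all subjects who have received at least one dose of CBP-201 from Stage 1 to Stage 2" and the period as "From the first dose of CBP-201 to the end of study". The text of the same section is worded differently: "SS3 will include all subjects in SS1 and SS2 who have received at least one dose of the study drug".

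**Tables run on SS3.** SAP 7.5.3 (laboratory) and 7.5.4 (ECG) both state: "Analysis will be performed based on SS1, SS2 and SS3". Both then drop by-visit analysis for SS3. What remains is the pre- versus post-treatment shift tables for laboratory tests and ECG, and the counts of QTcF increases above 30 and 60 ms from baseline. Neither section says which baseline these use.

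**The concern.** SS3 is the set that collects all CBP-201 exposure. A change table on it should compare each subject's values on CBP-201 with the last value before CBP-201, and neither defined baseline does this for every subject.

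- **D1 value used.** For a placebo starter, 16 weeks of placebo lie between the baseline and the first CBP-201 dose. An abnormality that arises in those weeks and is still present later can be counted as a shift on CBP-201. The reverse can also happen: an abnormality present at D1, resolved by W16 and recurring on CBP-201 shows no shift.
- **W16 value used.** For a CBP-201 starter, the baseline is taken after 16 weeks on drug. A laboratory or QTcF change that CBP-201 caused in Stage 1 becomes part of the baseline. A CBP-201 starter who never enters Stage 2 has no such value.

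Because no baseline is assigned, two programmers could produce different SS3 tables from the same SAP.

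**Working it through.** **Step 1. Set each baseline against the first CBP-201 dose.** Visit days are from the protocol's Study Flow Chart; treatment paths are from SAP 3.1.

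| Subject in SS3 | First CBP-201 dose | First baseline (D1) | Second baseline (W16 pre-dose) |
|---|---|---|---|
| CBP-201 starter, enters Stage 2 | D1 | pre-CBP-201 | on drug |
| CBP-201 starter, stops in Stage 1 | D1 | pre-CBP-201 | does not exist |
| Placebo starter, enters Stage 2 | W16 (D113) | pre-placebo, D113 − D1 = 112 days earlier | pre-CBP-201 |

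The first-baseline wording names no drug. I read it as the first study-drug dose because it is contrasted with the first Stage 2 dose, because Protocol 12.5 has the same wording, and because Table 4 writes CBP-201 where it means CBP-201.

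**Step 2. Reproduce the plan's numbers.** Protocol 12.3 gives 170 CBP-201 and 85 placebo subjects, 15% dropout, and about 144 and 72 completers.
- 170 × (1 − 0.15) = 144.5
- 85 × (1 − 0.15) = 72.25

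Both agree with the plan.

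**Step 3. Size SS3.** Assume that every CBP-201 starter is dosed, that all dropout falls in Stage 1, and that all Stage 1 completers enter Stage 2.
- SS3 = 170 + 72.25 = 242.25, about 242
- First baseline is not pre-CBP-201: 72.25 / 242.25 = 29.8%
- Second baseline is not pre-CBP-201: 170 / 242.25 = 70.2%, made up of about 144 on drug and 170 × 0.15 = 25.5, about 26, with none

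Range of the 29.8% over assumed dropout rates:
- 0%: 85 / 255 = 33.3%
- 30%: 59.5 / 229.5 = 25.9%

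For the supplementary analysis with 75 more subjects (330 in total, assuming 2:1 and 15% dropout), it is 93.5 / 313.5 = 29.8%.

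**Step 4. Look at the SS3 columns of Table 4.** Every CBP-201 starter begins on Q2W. If subjects receive the treatment assigned:
- Columns 4 (Q4W) and 5 (Q4W then Q2W) can contain only placebo starters. Under the D1 baseline they rest entirely on a pre-placebo value.
- Columns 2 (Q2W then Q4W) and 3 (Q2W, Q4W, Q2W) can contain only CBP-201 starters. Under the W16 baseline they rest entirely on an on-drug value.
- Column 1 (Q2W) mixes both kinds of starter.

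Either single choice makes the columns non-comparable.

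**Step 5. Check that the right values exist.** Protocol 6.2.2.1 (D1 pre-dose) and 6.2.2.4 (W16 pre-dose) both schedule safety laboratory tests and a 12-lead ECG.

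**The case against.** The strongest reply is that the SAP leaves the SS3 baseline unspecified and does not prescribe a wrong one. SAP 7.1 ties its two baselines to changes at each visit, and SS3 has no by-visit analysis. The shift tables speak of pre-treatment results, which for a set that begins at the first CBP-201 dose could be read as pre-CBP-201. That stands. A reader might infer that placebo-period changes will be reported as CBP-201 changes; the documents do not support that, since it depends on a choice the SAP does not make.

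Second, counting begins at the first CBP-201 dose, so a transient placebo-period change is not counted. After W16, laboratory tests resume at W24, and scheduled ECGs are only at W52 and W60, or at early termination (Protocol 6.2.3.2, 6.2.4 and 6.2.5). This also stands, and it limits the QTcF effect in particular.

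Third, each subject who enters Stage 2 has a correct value in one of the two baselines. Stage 1 changes on CBP-201 are also shown in SS1, against concurrent placebo and from the Stage 1 pre-dose baseline. The QTcF counts above 450, 480 and 500 ms need no baseline. Protocol 12.8 puts safety analyses on SS1 or SS2 and adds SS3 only for AEs. All of this bounds the consequence.

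What survives is that the SS3 shift tables and QTcF-increase counts need one baseline per subject, and neither defined baseline suits everyone. Reading pre-treatment as pre-CBP-201 would cure the shift tables but leaves the QTcF-increase counts open, and it is only one of the possible readings.

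**Conclusion.** The point holds in this form: SS3 has no baseline defined as the last value before the first CBP-201 dose, and no baseline is assigned to its shift tables and QTcF-increase counts.

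- If the D1 value is used, about 72 of 242 SS3 subjects (30%) and all of columns 4 and 5 are on a pre-placebo baseline.
- If the W16 value is used, about 144 CBP-201 starters are on an on-drug baseline and about 26 have none.

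The D1 value is the likelier default, because the W16 value is missing for CBP-201 starters who stop in Stage 1. These figures rest on the 15% dropout, all of it in Stage 1, and on every completer entering Stage 2. They count subjects whose baseline is not the pre-CBP-201 value. They do not count misattributed results, which the documents give no means to estimate.

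A reader might conclude that the SS3 laboratory and ECG tables are wrong whichever baseline is taken. That goes too far: each choice is right for one kind of starter and unsuitable for the other. The controlled SS1 comparison, the AE tables, power and type I error are unaffected. The correction should still be made, because the affected tables summarise laboratory and ECG change over the whole of CBP-201 exposure.

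**What to change.** Add to SAP 7.1: *For SS3, baseline is the last available value before the subject's first dose of CBP-201 (D1 for subjects starting on CBP-201, W16 pre-dose for subjects starting on placebo).* Name this baseline in SAP 7.5.3 and 7.5.4 for the SS3 shift tables and the QTcF-increase counts.

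In the same edit, reconcile the SS3 definitions: the text of section 6 and SAP 7.3.3 require a dose of study drug, while Table 4 requires a dose of CBP-201. Under the study-drug wording, placebo subjects who stop in Stage 1 (about 85 − 72 = 13) could enter SS3 without ever receiving CBP-201, and the new baseline would not exist for them.

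The cost is one sentence, two cross-references and one extra derived baseline flag. No new data are needed.
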